2.9.5 Other analysis

The concomitant medications, including those for target ulcers and non-target ulcers, will be

[REDACTED]

[REDACTED]

3 STUDY POPULATION

3.1 Definition of Subject Populations

All subjects who have procedures completed at Visit BS are considered study participants. The following subject populations are defined to assess the safety and efficacy of TTAX01 with SC.

Safety Population

The safety population is defined as all subjects who are enrolled and who have received at least one treatment of the investigational product.

Intention-to-treat (ITT) Population

This population is defined as all subjects who are enrolled to receive treatment. The ITT population is the primary population for efficacy evaluation in this study. The ITT population will be identified and finalized before the database is locked.

Per-Protocol (PP) Population

This population is defined as sub-population of the ITT population. The PP population is the secondary population for efficacy evaluation in this study. The detailed criteria of the PP population will be provided in a separate "Data Standards" document completed prior to data base lock.

3.2 Screening and Enrollment

An enrollment summary including the number of subjects screened, enrolled, and completed treatment will be presented for all screened subjects and by site (Table 1.1.1). The number of subjects enrolled (i.e., study participants or ITT population) will be summarized for each post-debridement ulcer size group and overall (Table 1.1.2). The number of subjects treated (i.e., the safety population) will be summarized for each post-debridement ulcer size group and overall (Table 1.1.3). The number of treated subjects terminating from treatment will be summarized for each group (Table 1.1.4).

3.3 Population Demography

For ITT and safety populations, descriptive summaries of demography and baseline characteristics will be presented for each group and overall to establish baseline comparability (Tables 1.2.1 to 1.2.2).

Demography includes age in years (continuous and categorical 18 to 39, 40 to 49, 50 to 59, 60 to 69, 70+), gender, race, ethnicity, weight, and height. Demography will also be listed for all study participants (Listing 1).

3.4 Disease Characteristics and Prior Treatment

For ITT and safety populations, descriptive summaries of baseline index ulcer characteristics will be presented for each group and overall to establish baseline comparability (Tables 1.3.1 to 1.3.2).

The size and duration and other characteristics of index ulcer will be listed for all subjects (Listing 1).

Primary therapy used for treatment of DFU prior to participating in the study will be listed for all subjects (Listing 1).

3.5 Medical History

Medical history will be listed in CRF data tabulation.

3.6 Disposition of Study Participants

Subject disposition including completion and discontinuation along with CRF-based termination reason will be summarized for ITT population and safety population (Tables 1.4.1 to 1.4.2). Subjects' early termination details will be listed for all subjects (Listing 2).

Subjects' TTAX01 treatment and date will be listed for all subjects enrolled (Listing 3).

3.7 Protocol Deviations and Violations

A summary of protocol deviation and violations will be provided for ITT population (Table 1.5.1). Subjects who are enrolled to receive treatment in the study and included in the ITT population, but do not have post-baseline status of ulcer closure will be listed for subjects enrolled (Listing 4).

Subjects who are included in the ITT population, but not included in the PP population due to either protocol violations or other documented reasons will be listed for all subjects excluded from the PP population (Listing 5). Major protocol violations may include the following:

- The subject fails to meet all inclusion/exclusion criteria and receives no waiver for entering into the study;
- The subject is terminated for protocol violations.

4 EFFICACY EVALUATION

4.1 Datasets Analyzed

The ITT population is defined as the primary efficacy population, and the PP population as the secondary efficacy population. Both populations will be identified and finalized before the database is locked. The definitions of the two populations are provided in Section 3.1.

4.2 Treatment Compliance

The compliance rate of SC treatment will be summarized by treatment group and demographic parameters for the ITT and safety populations (Tables 1.5.2 and 1.5.3).

4.3 Data Missing and Imputation

Summary of the observed data missing and imputation performed will be reported for index ulcer closure status, the primary efficacy measure, of the ITT population in Table 1.6.1.

4.4 Baseline Measures

Descriptive statistics of the index ulcer area, depth, and volume at baseline will be summarized by treatment for the ITT and safety populations (Tables 1.3.1 and 1.3.2).

4.5 Efficacy Results and Tabulations

4.5.1 Results of primary efficacy analysis

Descriptive and inferential statistics on the ITT population of the proportion of subjects with complete ulcer closure over the treatment period will be presented in Table 2.1.1.

For the PP population, the results of the same proportion analysis on the number of subjects with complete ulcer closure will be presented in Table 2.1.2.

The by-site summary of descriptive statistics of the number of subjects with complete ulcer closure will be presented in Table 2.1.3 for pooled sites and in Table 2.1.4 for original sites.

Individual subjects' primary efficacy data (i.e., complete ulcer closure), ulcer area measure and ulcer closure status at each visit, with and without imputation, will be listed by treatment for the ITT population (Listing 6).

4.5.2 Results of secondary efficacy analyses

Descriptive and inferential statistics on the ITT population of the number of days to complete ulcer closure will be presented in Table 2.3.1 for Cox regression analysis. The resultant probability of subjects with index ulcer open over the 16-week treatment period and estimated median time to ulcer closure will be reported in Table 2.3.2. For the PP population, the results of the same Cox regression analysis on the number of days to complete ulcer closure will be presented in Table 2.3.3 and Table 2.3.4.

Descriptive and inferential statistics on the ITT population of the proportion of subjects with complete ulcer closure for each post-baseline treatment week will be presented in Table 2.1.1.

Descriptive and inferential statistics on the ITT population of percent change of index ulcer parameters (ulcer area, depth, and volume) and percent of granulation tissue coverage at each treatment visit will be presented in Tables 2.4.1 thru 2.4.4.

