These 31 patients included 26 males and 5 females with an age of  $58.3 \pm 12.9$  years. The majority of patients treated were Caucasian (12/31) or African-American (10/31). Overall, these patients presented with multiple co-morbidities leading to the development of chronic, non-healing ulcers. Among the most significant co-morbidities were diabetes (26/31), hypertension (23/31), peripheral vascular disease (16/31), renal failure (12/31), and coronary artery disease (9/31). All 31 patients had histopathological evidence of osteomyelitis and carried a number of risk factors such as ischemia (i.e. gangrene (n=17), ischemic ulcers (n=24), previous partial amputation on the study leg (n=9), and previous revascularization attempt (n=1)) and infection (including osteomyelitis (n=33) and cellulitis (n=7)). The average ulcer size was  $15.6 \pm 17.7 \text{ cm}^2$  (0.4 - 74  $\text{cm}^2$ ).

Six of the 33 ulcers were lost to follow up during the course of the treatment including 1 patient who died of causes unrelated to product treatment. During the follow-up period, 26 of the remaining 27 wounds (96.3%) achieved complete wound closure. The overall clinical efficacy is reflected by complete healing in 22/27 (81%) at 24 weeks and 96% (26/27) at 44 weeks. For the 26 wounds that completely healed, the average time to wound closure was  $16.0 \pm 9.3$  weeks (range: 4 – 44 weeks) by one application in 21 wounds and 2 applications in the remaining 5 wounds, with the second application being applied from 4 – 10 weeks after the initial application. The patient with the non-healing wound went on to receive a below the knee amputation due to complications related to the wound and other co-morbidities, resulting in an amputation rate of 3%.

In summary, the above data support the feasibility of conducting a Phase 2 multiple-center open label pilot trial to examine TTAX01’s efficacy in promoting healing of complex non-healing diabetic foot ulcers with high risk factors of [1] ulcer depth indicating exposed bone, tendon,

muscle and/or joint capsule and [2] clinical suspicion of osteomyelitis, so as to reduce the likelihood of ulcer-related complications including limb amputation.

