### 3 OBJECTIVES AND ENDPOINTS

OBJECTIVES	ENDPOINTS	JUSTIFICATION FOR ENDPOINTS
Primary		
To examine the safety and estimate the efficacy of TTAX01 plus standard care (SC) in achieving complete wound healing of complex non-healing diabetic foot ulcers with high risk factors of [1] ulcer depth indicating exposed bone, tendon, muscle, and/or joint capsule and [2] clinical suspicion of osteomyelitis	Proportion of subjects with complete wound healing over the 16-week treatment period, defined as complete epithelialization with no drainage and no need for a dressing, confirmed at two visits, two weeks apart, and a biweekly end of treatment visit for a confirmatory duration of 4 weeks	Per FDA 2006 Guidance on endpoints for wound healing trials
Secondary		
To examine additional efficacy endpoints related to wound healing	
 
• Time in number of days to complete wound closure over the 16-week treatment period, starting from enrollment to the time of the initial observation of wound closure
 
• Proportion of subjects with complete wound closure at each of the 16 treatment weeks
 
• Percent change in the wound surface area (<math>\text{cm}^2</math>) at each visit from baseline for assessing the rate of wound closure in area
 
• Percent change in the wound volume (<math>\text{cm}^3</math>) at each visit from baseline for assessing the rate of wound closure in volume
 
• Percent change in the wound depth (cm) at each visit from baseline for assessing the rate of wound closure in depth
 
• Percent of index wound covered by the granulation tissue at each visit for assessing the rate of wound closure in granulation tissue
 
• Proportion of subjects achieving complete wound closure in subjects with pathologically confirmed osteomyelitis
 
	Time to heal is an alternative endpoint per the 2006 Guidance  Typical alternative to Cox proportional hazard  Wound area reduction may allow surgical closure  Alternate view of healing progress  Alternate view of healing process  Alternate view of wound healing process  Subset analysis
To examine the effect of therapy on ulcer-related complications (safety)	• Proportion of subjects who experience ulcer-related complications (e.g., life-	Relevant safety measures

OBJECTIVES	ENDPOINTS	JUSTIFICATION FOR ENDPOINTS

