and completion of debridement. Systemic antibiotics will be given empirically, with adjustments made on the basis of culture and sensitivity results. New or recurrent infections will be managed with additional debridement and adjustment or addition of appropriate systemic antibiotics. The test article, TTAX01, will be surgically fixed using sutures or staples to the debrided wound bed at baseline and again at 4 week intervals over the 16-week treatment period for wounds that do not show evidence of healing. For wounds that do show evidence of healing, additional applications of TTAX01 will be withheld, based on observations from retrospective case series (refer to Section 2.3.2)

Subjects whose wounds close prior to 16 weeks will move directly to a 2-week confirmation of closure. Subjects whose wounds have not closed by the end of 16 weeks will exit the trial.

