### 7.2 PARTICIPANT DISCONTINUATION/WITHDRAWAL FROM THE STUDY

All subjects have the right to discontinue the trial at any time. The Investigator may also withdraw a subject from the trial at any time if they deem it medically necessary. The reason for discontinuation should be documented and trial staff should attempt to bring the subject in for an Early Termination Visit and perform all applicable assessments as appropriate listed under the End of Treatment Period Visit (Visit 19) for discontinuations that occur during the Treatment Period.

Subjects may be discontinued from the trial for the following reasons:

- Adverse Event (including illness)

- Subject withdrawal of consent
- The Sponsor or Investigator terminates the trial
- Lost to follow-up
- Product-related > Grade 2 skin or systemic allergic reaction
- Ulcer-related complications (i.e., life-threatening, infection-related sepsis complications)
- Subsequent limb amputation (i.e., full amputation involving the index ulcer anatomic location)

In the event of a subject's withdrawal, the Investigator will promptly notify the medical monitor and will make every effort to complete all procedures at either the End of Treatment Period Visit. Even if removed subjects have been removed from the trial or if an adverse event remains ongoing, Investigators should follow up with subjects as per their standard medical practice.

Discontinued subjects will not be replaced. Simultaneous screening at multiple sites may result in an allowable modest over-enrollment.

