2.8 Handling of Missing, Incomplete, and Repeat Data

Primary Efficacy Endpoint: Confirmed complete ulcer closure

Secondary Efficacy Endpoint: Time to complete ulcer closure

[REDACTED]

Secondary Efficacy Endpoint: Complete ulcer closure at each treatment week:

[REDACTED]

Secondary Efficacy Endpoint: Ulcer and granulation tissue measures at each treatment visit

[REDACTED]

Safety Endpoints:

[REDACTED]

[REDACTED]

[REDACTED]

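### Time to closure: the open-ulcer probability and median come from a Cox model in a one-arm trial, and closure is overstated if amputated or deceased subjects are censored

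*SAP*

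**What the plan says.** - **Method.** SAP 4.5.2 states that the "number of days to complete ulcer closure will be presented in Table 2.3.1 for Cox regression analysis". Its next sentence sends "The resultant probability of subjects with index ulcer open over the 16-week treatment period and estimated median time to ulcer closure" to Table 2.3.2. Tables 2.3.3 and 2.3.4 repeat both for the per-protocol population.
- **Design.** SAP 2.4 confirms a single treatment arm without randomization.
- **Event and clock.** Protocol section 3 counts days "starting from enrollment to the time of the initial observation of wound closure".
- **End of observation.** Protocol 4.1: "Subjects whose wounds have not closed by the end of 16 weeks will exit the trial".
- **Events that make closure impossible.** Protocol 7.2 lists among the reasons for discontinuation "Subsequent limb amputation (i.e., full amputation involving the index ulcer anatomic location". SAP 2.9.4 analyses time to first amputation or death by Kaplan-Meier, as a safety outcome. No readable text links those events to the closure analysis.
- **Companion figure.** SAP 4.5.2 also reports the ITT proportion closed at each treatment week, in Table 2.1.1.
- **What cannot be read.** SAP 2.8 has an entry headed "Secondary Efficacy Endpoint: Time to complete ulcer closure", but the rule beneath it is blacked out. The secondary methods in SAP 2.9.2 are not shown either.

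**The concern.** Two features of the planned output deserve attention.

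First, the curve comes from a Cox model although there is no treatment contrast to estimate. Without covariates, the Cox-derived curve is in essence an ordinary survival curve. With covariates such as ulcer size, it depends on the covariate values at which it is drawn and need not agree with the observed proportion closed.

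Second, a survival curve treats a censored subject as still able to close later. That is reasonable for someone who moves away. It is not reasonable for an ulcer whose site has been amputated, or for a subject who has died. These are competing events. Censoring them makes 1 minus the open probability larger than the share of subjects who closed. Table 2.3.2 would then show more closure than the weekly ITT proportions in Table 2.1.1, with no explanation given.

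The trial enrols ulcers at high risk of amputation, and Protocol 4.2 intends its response estimates to inform power calculations for a larger controlled trial, so an upward bias could carry forward. A further practical point is that the readable text does not say what is reported if fewer than half of the ulcers close by week 16 and no median exists.

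**Working it through.** **Inputs from the documents.** N = 36 and dropout of about 10% (Protocol 9.2). In the closest earlier series, "complete healing in 22/27 (81%) at 24 weeks and 96% (26/27) at 44 weeks"; the 26 healed wounds took 16.0 ± 9.3 weeks, range 4 to 44; six of 33 ulcers were lost; the amputation rate was 3% (Protocol 2.2). The table in Protocol 2.3.2 gives 26/33 healed for that series, 28/32 (13.8 ± 1.95 weeks) for a second and 51/64 (5.53 ± 3.93 weeks) for a third.

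**Assumptions.** Constant hazards, 50% closed by week 16, and competing-event rates of 3% to 20%. The documents state no 16-week closure or competing-event rate for this trial.

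**1. Reproduce the dated figure.** Fit a lognormal to the mean and SD among healed wounds:
- σ² = ln(1 + (9.3/16.0)²) = 0.291, so σ = 0.540; μ = ln 16.0 − 0.291/2 = 2.627.
- Share of healed wounds closed by week 24: Φ((ln 24 − 2.627)/0.540) = 0.846.
- Times 26/27: 0.815. The series reports 22/27 = 0.815, so the fit reproduces it. A gamma fit gives 0.795.

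**2. Excess from censoring competing events.** Let c be the true proportion closed and a the proportion amputated or dead by week 16. The total cumulative hazard is L = −ln(1 − c − a), the closure part is L·c/(c + a), and the censoring curve gives 1 − exp(−L·c/(c + a)). With c = 0.50:

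| a | L | closure part | censoring curve | excess |
|---|---|---|---|---|
| 3% | 0.755 | 0.712 | 50.9% | +0.9 points |
| 5% | 0.799 | 0.726 | 51.6% | +1.6 points |
| 10% | 0.916 | 0.764 | 53.4% | +3.4 points |
| 20% | 1.204 | 0.860 | 57.7% | +7.7 points |

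A simulation of 36 subjects with weekly visits, lognormal closure times and competing events at random times (4,000 runs) agrees broadly: about 1 point on average at 3%, and more than 6 points at 20%.

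The 3% row uses the series' amputation rate. Adding its one death, counted as one ulcer, gives 2/33, about 6%. The 10% row is what follows if the whole dropout allowance consisted of competing events. The 20% row is an assumed upper case.

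**3. Is the median reached by week 16?** Share of healed wounds closed by week 16: Φ((ln 16 − 2.627)/0.540) = 0.606.
- Base 26/27 (losses left out): 0.606 × 26/27 = 58% (gamma 56%), median near week 14.2. Chance that at least 18 of 36 close: 88% (gamma 80%).
- Base 26/33 (losses counted as never closing): 0.606 × 26/33 = 48% (gamma 45%), median near week 16.7. Chance: 46% (gamma 35%).
- Second series: 76% closed by week 16 if 1.95 is an SD, 59% to 62% if it is a standard error. Third series: 78%.

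**The case against.** **The rule may already be right.** SAP 2.8 has a dedicated entry for time to closure, the abbreviations include last observation carried forward and worst case, and SAP 4.3 and 4.5.1 refer to imputation. If amputated and deceased subjects are carried as open to week 16, the excess disappears. This objection stands. A reader might infer that the plan does overstate closure; the documents do not show that, and text missing through redaction is not a fault.

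**The size may be small.** At the 3% amputation rate of the closest series the excess is about 1 point. An assumed 15% would give L = −ln 0.35 = 1.050, a closure part of 0.808 and 55.4%, or +5.4 points, but 15% is above the plan's entire dropout allowance and appears nowhere as an expected rate. Even 3.4 points is about one subject in 36 (0.034 × 36 = 1.2), against a 95% half-width of 1.96 × √(0.25/36), about 16 points. On the other side, Protocol 2.1 cites amputation rates as high as 51% in limb-threatening infection, without a time frame, so a rate above 3% cannot be excluded. Bias also differs from imprecision, because it carries into a later trial's planning.

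**The median.** It is tempting to say that the median will probably not be reached. That needs the 26/33 base, on which six lost wounds never close. An estimator that censors losses corresponds to 26/27, which gives 58%. The other two series are higher, though their populations are less close to this one, and the closest series had larger wounds (mean 15.6 cm² against 1 to 10 cm² here). Censoring competing events also makes a reported median more likely, not less: in the simulation with 20% competing events on the 26/33 base, the Kaplan-Meier median was reached in about 40% of trials, against 11% to 19% by cumulative incidence.

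**Other outputs help.** The weekly ITT proportions and the separate amputation-or-death analysis let a careful reader see the discrepancy. They do not explain it, and they do not correct the curve. Cox may also have a descriptive use, since the SAP groups many tables by post-debridement ulcer size.

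**Conclusion.** The point holds in conditional form. Cox regression is an indirect source for a one-arm closure curve. If index-site amputation or death is censored, the curve overstates closure by about 1 point at 3% competing events, 3 at 10% and 8 at 20%, given 50% closure and constant hazards. Whether it does so depends on rules in SAP 2.8 and 2.9.2 that cannot be read.

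Whether the median is reached by week 16 is uncertain. The closest series implies 48% to 58% closed, depending on how its losses are counted and on a lognormal shape. The documents do not support calling a missing median probable.

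The comparison with Table 2.1.1 isolates competing events. Ordinary dropout can also separate the two tables, depending on the imputation rule. This is a cheap improvement to a secondary analysis in a descriptive pilot and does not touch the primary proportion.

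**What to change.** Confirm what SAP 2.8 and 2.9.2 do with subjects amputated at the index location or deceased. Unless they already cover it:

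1. In Tables 2.3.2 and 2.3.4, replace the Cox-derived curve with the nonparametric (Aalen-Johansen) cumulative incidence of confirmed closure with 95% confidence interval, treating index-site amputation and death as competing events.
2. Keep Cox in Tables 2.3.1 and 2.3.3 only as a descriptive look at covariates such as ulcer size.
3. Beside the median, give the 25th percentile and the restricted mean weeks open to week 16, and say that the median is reported as not reached when it is. Define the restricted mean as the area above the cumulative incidence curve, so that time after amputation or death counts as not closed.
4. Align SAP 2.8, 2.9.2 and 4.5.2 on this rule.

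The cost is a few lines of SAP wording and standard software output. The closure curve may look slightly less favourable and a median may be reported less often. If no competing event occurs, the cumulative incidence equals the ordinary nonparametric closure curve and nothing is lost.

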5 SAFETY EVALUATION

For safety evaluation, the safety population as defined in Section 3.1 will be utilized to conduct safety analyses among treatment groups.

5.1 Extent of Drug Exposure

Exposure to study medication will be tabulated by treatment in Table 3.1.1 for total number of SC treatments received and in Table 3.1.2 for TTAX01 application received, using the following categories: 1-2 applications, 3-4 applications, 5-6 applications, 7-8 applications, 9-

10 applications, 11-12 applications, 13-14 applications, and 15-16 applications. The tabulations will be done for the safety population, and for man and woman, separately.

Individual subjects' treatment exposure (applications) will be listed by treatment regimen for the safety population (Listing 3).

